is expected to be improved understanding of how biomechanical, neuromuscular, and somatosensory mechanisms influence symptom severity in adults with CMC OA. This contribution is *significant* as it directly addresses the primary barrier preventing the design of new, optimal treatments: the mechanisms that influence the severity of CMC OA have not been fully identified, and therefore cannot be clinically targeted.

[figure not shown]

Figure 2. To alleviate CMC OA symptoms, we must understand multiple mechanisms.

5. SPECIFIC AIMS:

Individuals with symptomatic thumb carpometacarpal osteoarthritis (**CMC OA**) can lose up to 50% of hand function.² Surgical treatments aim to restore function and reduce pain by eliminating instability at the CMC joint. However, there are eight different surgeries commonly used, and no consensus on how to optimally choose between them.³ Treatment is also challenging because the presentation of symptoms is highly variable.⁴ For example, 33% of postmenopausal women have radiographic evidence of thumb CMC OA,⁵ yet only 5% of all women visit the doctor with symptoms.⁴ Some individuals may employ unique coping mechanisms that prevent development of pain and functional loss, while others may simply use over-the-counter medications to avoid the doctor. Regardless, very little is known about how an individual's symptoms relate to the underlying osteoarthritic disease. My *long-term goal* is to design effective, targeted treatments for individuals with CMC OA. As a critical step toward this goal, the *objective of this proposal* is to elucidate the biomechanical, neuromuscular, and somatosensory mechanisms that occur during aging and contribute to the symptomology of CMC OA. This objective will be accomplished through two aims:

Aim 1. Evaluate how muscle activity, joint kinematics, and CMC joint stability change in the presence of movement-evoked pain. Electromyography (EMG), joint kinematics, CMC joint stability, and movement-evoked pain during three functional tasks will be quantified in adults with end-stage CMC OA, age-matched controls, and young-healthy individuals. We *hypothesize* that greater levels of reported pain during task completion will be associated with increased muscle activity, larger joint angles, and decreased joint stability. Completion of this aim will quantitatively characterize biomechanical and neuromuscular mechanisms that influence CMC OA symptomology.

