Aim 2. Quantify the relationship between function, pain symptomology, and disease severity. Hand function, clinical and experimental pain, and disease severity will be measured in adults with end-stage CMC OA, age-matched controls, and young-healthy individuals. We *hypothesize* individuals with CMC OA will demonstrate greater functional deficits and higher experimental pain sensitivity than age-matched controls and young-healthy individuals. Additionally, in individuals with CMC OA, we hypothesize that functional loss will be associated with higher clinical pain, but not necessarily higher disease severity. Completion of this aim will comprehensively and quantitatively characterize the multi-faceted symptomology of CMC OA and provide insights into the somatosensory mechanisms affecting this disease.

6. RESEARCH PLAN:

Sample Size & Justification: A total of 60 subjects will complete the proposed research study: 20 individuals with end-stage CMC OA, 20 age-matched controls, and 20 young-healthy individuals. These subjects will represent the racial and ethnic diversity of the state of Florida. Vulnerable populations including pregnant women and prisoners will be excluded. All subjects will be between the ages of 18 to 90. Specifically, the end-stage CMC OA cohort and age-matched controls will be between the ages of 40 to 90 as CMC OA is most prevalent in older adults. While the young-healthy cohort will be between the ages of 18-39. A power analysis ($\alpha = 0.05$, $1-\beta = 0.80$) to detect 20% differences in pinch strength between groups required 15 individuals per cohort. Due to including a young-healthy cohort and to prevent erroneous inferences to occurs after multiple comparisons, 20 individuals per cohort will be recruited. Note, pinch strength was the only relevant variable for which standard deviations could be consistently estimated from the literature.^{23, 36} Thus, an important outcome of this pilot project will be the data necessary to robustly estimate sample sizes for future studies. For reference, prior studies indicate that individuals with early-stage CMC OA have 20-30% less pinch strength than controls.^{23, 36}

A summary of inclusion and exclusion criteria are provided below:

Inclusion Criteria:

CMC OA Subjects:

- female between the age of 40 to 90 years
- end-stage CMC OA diagnosed by a board-certified clinician

Age-Matched Control:

- female between the age of 40 to 90 years
- no joint or muscle pain in the hand or wrist

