The proposed human subject research will occur during three sessions. The first session (focused on biomechanics data for Aim 1) will include motion capture, electromyography (EMG), movement-evoked pain testing. This session is expected to last no more than 4-hours. The second session (focused on somatosensory data for Aim 2) will include experimental pain testing, clinical pain testing, and clinical outcome measures. If needed, the clinical outcome measures can be completed in the first session as it is at no risk to the patient or the study. This session is expected to last 2-hours. The third session (medical imaging for Aim 2) will involve recording plain film radiographs. This session is expected to last less than 1-hour. Sessions can be scheduled consecutively on the same day or as separate study visits, based on the subject's schedule and availability. Sessions can also be completed in any order. Detailed descriptions of each session is provided below:

Session I – Biomechanics Testing Session (Collection of Data for Aim 1).

Location: All biomechanics testing will occur in [name] Biomechanics Laboratory, located in Room 510 of the New Engineering Building ([name]). This laboratory is specifically designed for biomechanical testing and human subject experiments. It is a limited-access lab, meaning that only [name] students and collaborators have access. All individuals with access have completed human subjects research training. During testing, only members of the IRB-approved Study Team will be involved in experimental data collection. A sign that reads "Experiment in Progress" will be posted on the door during data collection to ensure subject privacy is maintained.

Testing Procedures: All participants will be asked to wear short sleeve or sleeveless tops during testing. Participants will have the option to wear their own clothing or clothing provided by the lab. Participants will also be given the option to change into clothing in a private changing area after arrival at the lab.

Upon arriving at the Musculoskeletal Biomechanics Lab, participants will be asked to provide basic demographic (age and sex) and anthropometric (height, weight, limb length) data. Following collection of this information, biomechanical data will be collected using skin-marker motion capture, electromyography (EMG), and movement-evoked pain testing.

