During testing, participants will be asked to perform range of motion tasks (e.g., circumduction of the CMC joint) as well as strength tasks (e.g., lateral pinch and opposition pinch) at varying effort levels (maximal and sub-maximal). Each task and effort level will be repeated at least twice. Skin-marker motion capture, EMG, and movement-evoked pain data will be collected during each task as described below:

Skin-Marker Motion Capture & Force Sensors

Skin-marker motion capture involves placing reflective markers on palpable boney landmarks, such as the distal radial styloid. These reflective markers are secured to the subject's skin using adhesive tape. Reflective markers will be placed across the hand and arm following the guidelines of the International Society of Biomechanics. Locations of the markers will be recorded during completion of the tasks using a 12-camera Vicon Vero motion capture system. During testing, the forces produced by the thumb will be recorded using custom force sensors. These data will provide a kinematic description of how the thumb, wrist, and arm move during the recorded tasks as well as kinetic data describing the forces produced. These data will also be used in the musculoskeletal simulations to calculate CMC joint contact forces.

Intramuscular and Surface Electromyography (EMG).

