Most of the experimental procedures involved in this study have no greater than minimal risks. However, intramuscular electromyography (EMG), which involves insertion of fine wire needle electrodes, poses slightly more than minimal risk. All procedures are described below:

Activities Performed During Motion Capture. Participation in the motion capture study should not cause pain or discomfort beyond what is experienced in routine, daily life or a standard clinical evaluation during a visit to the doctor. Nonetheless, we will exclude research subjects who are unwilling or unable to perform the activities to ensure that it poses no substantial additional risk or causes no substantial pain to our subjects.

Skin-Marker Motion Analysis. Skin-marker motion analysis poses minimal risk to subjects. Reflective markers are secured to the skin using adhesive tape. Removing this tape may cause mild discomfort or skin irritation (i.e., redness). This discomfort is similar to that experienced when removing a bandaid.

EMG. Surface EMG poses minimal risk. The only known health risk is mild discomfort or skin irritation (i.e., redness) associated with removal of the surface electrodes. Rare, but possible risks of intramuscular (or fine wire) EMG include inflammation, infection, bleeding, and/or fainting. Damage to nerve or blood vessels from the wire is also possible, although rare. Mild discomfort associated with placement of the intramuscular EMG electrode is possible. We will minimize risks by having only trained research staff insert intramuscular electrodes. Ultrasound guidance will also be utilized to assist with needle placement around sensitive anatomy. Additionally, subjects will be given the option of stopping needle insertion at any time. Subjects will be fully compensated for the biomechanics session, even if they choose to stop EMG needle insertion prior to all electrodes being placed.

Quantitative Sensory Testing. QST is generally considered safe. However, participants will experience some pain or discomfort. Due to the pressure pain procedure (mechanical stimuli), there is a slight chance that a bruise may form as a result of the pressure pain procedure. Also, some patients may experience after-sensations after application of pressure stimuli to their symptomatic thumb, though this is expected to be brief in duration. Also, this risk is diminished

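### The risk section excludes subjects unwilling or unable to do the motion-capture activities; this rule is absent from the eligibility list and can remove the most impaired CMC OA subjects

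*Protocol*

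**What the plan says.** The rule stands in section 7 (Possible Discomforts and Risks) of the protocol, under Activities Performed During Motion Capture: "we will exclude research subjects who are unwilling or unable to perform the activities". Its stated purpose follows at once: "to ensure that it poses no substantial additional risk or causes no substantial pain to our subjects". The sentence before it expects that taking part "should not cause pain or discomfort beyond what is experienced in routine, daily life or a standard clinical evaluation".

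The activities are described in section 6 under Session I. They are range-of-motion tasks of the thumb and pinch tasks at maximal and sub-maximal effort. The CMC OA cohort is defined there as end-stage disease, while both control cohorts must be free of hand and wrist pain. The inclusion and exclusion lists in section 6 contain no criterion on ability or willingness to perform these tasks.

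The variables involved are central to section 5. Aim 1 expects that "greater levels of reported pain during task completion will be associated with increased muscle activity". Aim 2 expects larger functional deficits in CMC OA than in controls and, within the CMC OA cohort, "we hypothesize that functional loss will be associated with higher clinical pain, but not necessarily higher disease severity".

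Section 6 (Research Approach) places motion capture in Session I, sensory testing, questionnaires and function tests in Session II, and radiographs in Session III. It adds: "Sessions can also be completed in any order".

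**The concern.** The object of the exclusion is the research subject, not the task or the session. Someone with end-stage disease who cannot do a maximal pinch would, on the natural reading, also be lost to the questionnaires, sensory testing and radiographs, none of which need that pinch. Being unable to do it is itself a form of the functional loss under study, so the rule selects on a study outcome. It formally covers all three cohorts, but would act mainly in one.

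Two consequences follow if it acts. The CMC OA mean moves toward the control mean, and the range of pain and function within the CMC OA cohort narrows, which weakens correlations.

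The rule is also badly placed. Because sessions may run in any order, a subject can be found unable after her Aim 2 data exist, and the protocol does not say whether those data are kept. Section 6 says that 60 subjects will complete the study. If excluded subjects are replaced by abler ones, the cohort size stays at 20 and the selection cannot be seen.

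**Working it through.** **The plan's own figure.** Section 6 states alpha 0.05, power 0.80, a 20% difference in pinch strength and 15 per cohort, with 20 recruited. It gives neither the SD nor the sidedness, so 15 cannot be verified. It can only be solved backwards. With a two-sided test, the normal approximation returns 15 when the SD is about 18.9-19.5% of the control mean. The noncentral t gives 18.87%, a standardised difference of 20 / 18.87 = 1.06. That SD is used below. With 20 per cohort and no exclusion, power is 0.904.

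**Assumptions, none from the protocol.** A fraction f of the CMC OA cohort, the worst on a selection variable, is removed. That variable correlates rho with the outcome, and the outcome is normal. Twenty per cohort are analysed, meaning that removed subjects are replaced; without replacement, power would be lower still.

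**Formulas.**
- z = the standard normal quantile at f; lambda = phi(z) / (1 - f)
- observed deficit = 20 - 18.87 x rho x lambda (in % of the control mean)
- OA variance ratio v = 1 - rho^2 x lambda x (lambda - z)
- pooled SD = 18.87 x sqrt((1 + v) / 2)
- power from the noncentral t with 38 df and noncentrality d / sqrt(2/20), where d = observed deficit / pooled SD

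**Two cases in full.**
- f = 0.05, rho = 0.3: z = -1.645, lambda = 0.1086. Deficit = 20 - 18.87 x 0.3 x 0.1086 = 19.4. v = 0.983, pooled SD = 18.79, d = 1.03, power 0.889.
- f = 0.20, rho = 1: z = -0.842, lambda = 0.350. Deficit = 20 - 18.87 x 0.350 = 13.4. v = 1 - 0.350 x (0.350 + 0.842) = 0.583, pooled SD = 16.79, d = 0.80, power 0.691.

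**Range.**

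| OA subjects removed | rho | Observed deficit (%) | Power |
|---|---|---|---|
| none | - | 20.0 | 0.904 |
| 5% | 0.3 | 19.4 | 0.889 |
| 5% | 1 | 17.9 | 0.869 |
| 10% | 0.5 | 18.2 | 0.855 |
| 10% | 1 | 16.3 | 0.821 |
| 20% | 0.3 | 18.0 | 0.844 |
| 20% | 0.5 | 16.7 | 0.800 |
| 20% | 1 | 13.4 | 0.691 |

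The rho = 1 rows treat inability as exact truncation on the outcome itself. For each fraction they bound the bias from above.

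**Within-cohort association.** Let u = sqrt(v) at rho = 1, so u = 0.900, 0.844 and 0.764 for 5%, 10% and 20% removed. If selection acts on one of the two correlated variables itself, a true correlation r is seen as r x u / sqrt(1 - r^2 + r^2 x u^2). An assumed r = 0.50 becomes 0.46, 0.44 and 0.40. Power at n = 20, computed as Phi(atanh(r) x sqrt(17) - 1.96), falls from 0.62 to 0.54, 0.49 and 0.42. This too is an upper bound on the attenuation for each fraction.

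**Planning use.** Section 6 names data for future sample-size estimates as an important outcome. The same u values mean that the OA SD could be understated by 10% to 24% at the bound.

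**The case against.** The strongest case on the other side has five parts.

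- *A pain criterion.* A reader might infer that anyone for whom the tasks would cause substantial pain is excluded, which would be direct selection on the Aim 1 exposure. The text does not support this. The phrase "causes no substantial pain to our subjects" states the purpose of the rule and sets no threshold. A willing and able subject with severe task pain stays in, and her pain is rated before, during and after each task. This objection stands in full.
- *Scope.* A reader might take removal from the whole study as settled. It is the natural reading of excluding research subjects, but the sentence sits under a motion-capture heading and could mean that part only. Section 7 lets a subject stop needle insertion and still be fully compensated for the session, which fits handling by procedure. So the scope is unclear, and that is itself a reason to fix the wording.
- *Occurrence.* A reader might infer that the rule will remove the most impaired subjects and shrink the effects. No exclusion rate is given, only everyday levels of pain are expected, a weak pinch is still a measurement, and unwillingness need not track impairment. What can be said is that the rule can do this.
- *Size.* The milder scenarios keep power at 0.80 or above. The protocol cites 20-30% pinch loss in early-stage disease, so 20% may be a low figure for an end-stage cohort. This stands against a claim of serious power loss, but it does not change the direction of the bias.
- *Remedy.* Rewording cannot create EMG, kinematic or task-pain data for a task not done. Session II also includes pinch, grip, thumb-motion and timed hand tests, so some Aim 2 function data may be missing as well. This stands, but the questionnaires, sensory testing and radiographs would still be retained.

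**Conclusion.** The point holds as a correctable weakness in the wording of the design. An ability-based exclusion appears only in the risk section, is missing from the eligibility list, has unclear scope, and depends on an outcome of the study in a way that falls mainly on one cohort. Any resulting bias runs toward smaller OA-versus-control deficits and weaker pain-function associations, provided that inability tracks impairment.

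The size cannot be known from the protocol. Under the stated assumptions, a 20% deficit would be seen as anything from 19.4% (a relative loss of 0.6 / 20 = 3%) to 13.4% (6.6 / 20 = 33%, an upper bound), with power between 0.89 and 0.69 against 0.90 without exclusion. The SD, the fraction removed, its correlation with the outcome and the correlation of 0.50 are all assumptions.

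**What to change.** Leave unchanged the decision not to perform or to stop a task, and the study physician's discretion in section 7 to exclude for excessive risk. Then:

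1. Reword the motion-capture paragraph of section 7 so that not performing a motion-capture task does not by itself exclude the subject from the other tasks or from Sessions II and III.
2. Reconcile that paragraph with the inclusion and exclusion lists in section 6, so that one rule governs enrolment.
3. State that Aim 2 data already collected are kept.
4. Record the reason for each task not performed, and report the number of such subjects by cohort.

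How a task not performed enters an analysis can be left to the SAP.

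The cost is a short wording change and one field on the data form. The downside is that some CMC OA subjects will lack EMG and kinematic data for a task, and Aim 1 stays limited to those able to perform it.

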Young-Healthy Subjects:

- female between the age of 18 to 39 years
- no joint or muscle pain in the hand or wrist

Exclusion Criteria:

All Groups:

- Pregnant women; minors (under age 18); mentally disabled; any persons incarcerated, on parole, on probation, or awaiting trial
- Individuals with concomitant musculoskeletal pathologies (other than osteoarthritis) in the hand or wrist, including distal radius fracture, contracture, trigger finger, and carpal tunnel
- Individuals with history of uncontrolled diabetes, rheumatoid arthritis, muscular dysfunction, or neurological disease

Recruitment:

The CMC OA subjects, age-matched control subjects, and young-healthy control subjects will be recruited, as described below:

CMC OA Subject Recruitment: Subjects with CMC OA will be recruited directly from the hand clinics at the UF Orthopaedics Sports Medicine Institute (OSMI). Specifically, a clinical member of the study team affiliated with the Department of Orthopaedics (e.g., [name]) will identify individuals who meet the inclusion criteria. These individuals will be asked at the end of their clinic visit if they are interested in learning more about the research study and potentially participating. At this time, the potential participant's contact information (name, e-mail, phone number) and preferred contact method (phone or e-mail) will be recorded. A member of the IRB-approved study team will then reach out to the potential participant by phone or e-mail to discuss the study and answer any questions. If the potential participant expresses interest, he or she will be e-mailed a copy of the informed consent document to review and discuss with their friends and/or family. The study sessions will also be scheduled at this time. Subjects will be consented in-person at the time of their first study session.

Age-Matched Control Subjects and Young-Healthy Subjects: Age-matched control subjects and young-healthy subjects will be recruited using the mechanisms listed below. It should be noted that individuals with CMC OA may also contact the study team via these mechanisms. However, the study team anticipates that these mechanisms will more readily identify age-matched control subjects:

- 1) Recruitment Flyer – An IRB-approved recruitment flyer will be posted around the University of Florida's campus and the Gainesville community in approved advertising

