locations. The flyer will provide potential participants with the information necessary to contact the Study Team by phone and/or e-mail.

- 2) Website Advertisement – An IRB-approved recruitment message will be posted on the Principal Investigator's Lab Website (<https://www.bme.ufl.edu/labs/[name]/get-involved/>) The recruitment message will provide potential participants with the information necessary to contact the Study Team by phone and/or e-mail.
- 3) Word of Mouth – The Principal Investigator and Study Team frequently share results from completed studies through invited talks, guest lectures in undergraduate and graduate courses, and community events. When discussing our human subjects research, one of the most commonly asked questions is whether there are opportunities to become involved as a study participant. Thus, we will share information about the study verbally with interested members of the community. When such verbal conversations take place, we will provide the potential participants with the information necessary to contact the Study Team by phone and/or e-mail. Scheduling and enrollment will occur at least 48 hours after the initial conversation and only after the potential participant has proactively contacted the Study Team.

Initial Contact with Study Team:

When a potential participant contacts the Study Team, we will follow-up with the potential participant by phone or e-mail. During that discussion, we will ask the following questions:

- a) Are you a female between 18 and 90 years old?
- b) Have you been diagnosed with arthritis in your hand or wrist?
- c) Do you currently have muscle or joint pain in the hand or wrist?
- d) Have you had any muscle or joint pain in your hand or wrist requiring medical attention or physical therapy in the last 6 months?
- e) Are you currently pregnant, mentally disabled, incarcerated, on parole, on probation, or awaiting trial?
- f) Do you have any systemic musculoskeletal, neurological, or autoimmune diseases, such as diabetes, rheumatoid arthritis, or stroke?

If a potential participant answers "yes" to question (a) and "no" to questions (b) – (f), then we will proceed with scheduling a study visit as an age-matched control subject.

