If a potential participant answers "yes" to question (a) – (b) and "no" to questions (c) – (f), then we will ask the following follow-up question: "What kind of arthritis have you been diagnosed with in your hand or wrist?" If the answer is thumb OA, we will proceed with scheduling a study visit as an CMC OA subject.

Otherwise, the potential participant will be informed that he or she is ineligible to participate.

To facilitate continued communication and follow-up, we will ask the potential participant what his or her preferred method of contact is and will record his or her name, phone number, and e-mail address during these initial conversations. We will use the e-mail address to provide the potential participant with an electronic copy of the informed consent form to review prior to his or her first visit. This copy of the informed consent form will be provided to the subject at least 24 hours prior to their scheduled participation. All research subjects will be consented in-person at the time of their first study session.

Enrollment & Informed Consent:

Prior to experimental data collection, each participant will be given the opportunity to review the informed consent form and study procedures in-person with a member of the study team. This discussion will include information on study purpose and procedures, benefits and risks, who to contact (study team, IRB, etc.), that participation is voluntary and participants can withdraw at any time, HIPAA and confidentiality, as well as cost and compensation. The participant will be given the opportunity to ask questions. After all questions have been answered, the participant will sign the informed consent form, documenting that they provide consent to participate as well as authorization to access their private health information as outlined on the informed consent form.

Research Approach:

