Motion analysis and EMG testing (Session I biomechanics testing) will take place in [name] Biomechanical Laboratory in the J. Crayton Pruitt Family Department of Biomedical Engineering. Only trained members of the research team will operate the motion capture and EMG systems. [name] has received training on insertion of fine wire EMG electrodes through the Gait & Clinical Movement Analysis short course. This training fulfills the classroom training requirements for clinicians and researchers in California, the state with the strictest fine wire EMG electrode laws. All fine wire needle electrodes will be placed following best practices to ensure safety and sterility.

The experimental pain procedures (Session II somatosensory testing) described in this application are widely used and safe. While they produce pain, risks to the subjects are minimal, because:

- 1) the pain is transient in nature, and generally subsides immediately after the procedure;
- 2) subjects are instructed that they may stop any procedure at any time with no adverse consequences; and
- 3) the level of pain experienced by subjects is below their tolerance level.

[name], who has extensive experience with experimental pain testing, and [name], who has extensive experience with clinical pain testing, will ensure all pain testing is completed in a safe and appropriate manner. Risks will also be minimized by adhering to our exclusion criteria, and the study physician ([name], co-mentor) will have full discretion to exclude participants for whom they feel there is excessive risk for participation.

8. POSSIBLE BENEFITS:

There are no direct benefits to subjects for participating in this study. However, the knowledge gained from this study will benefit society by providing new information regarding the mechanisms underlying CMC OA pain and disability.

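### Bleeding is a named risk of fine-wire EMG, but no listed exclusion criterion or phone question covers blood-thinning medicine or a bleeding disorder, and no stated step brings it to the physician first

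*Protocol*

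**What the plan says.** Section 7 (EMG) singles out intramuscular EMG as the procedure carrying slightly more than minimal risk. It states: "Rare, but possible risks of intramuscular (or fine wire) EMG include inflammation, infection, bleeding, and/or fainting". It adds: "Damage to nerve or blood vessels from the wire is also possible, although rare". Section 6 (Intramuscular and Surface Electromyography) plans these electrodes for nine thumb muscles and caps insertion attempts at three per muscle.

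On selection, section 6 introduces the criteria with "A summary of inclusion and exclusion criteria are provided below". Three exclusion bullets follow for all groups. The one on medical history reads: "Individuals with history of uncontrolled diabetes, rheumatoid arthritis, muscular dysfunction, or neurological disease". Under Initial Contact with Study Team, six questions, (a) to (f), are put to people who contact the team themselves. The closest to this point is (f): "Do you have any systemic musculoskeletal, neurological, or autoimmune diseases, such as diabetes, rheumatoid arthritis, or stroke". For a person who answers yes to (a) and no to the rest, the rule is: "then we will proceed with scheduling a study visit as an age-matched control subject". A self-referred person with diagnosed arthritis who answers no to (c) to (f) gets one further question, on the type of arthritis, and is booked as an OA subject if it is thumb OA.

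Section 7 (Minimizing Risks by Using Qualified Study Personnel) then states: "Risks will also be minimized by adhering to our exclusion criteria, and the study physician" has full discretion to exclude people at excessive risk.

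**The concern.** The protocol names a risk, then relies on its exclusion criteria and a physician's judgement to limit risk. The listed criteria do not address the factor most obviously tied to bleeding, and the physician can only act on what the physician knows.

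The gap is widest for self-referred controls, who come by flyer, website or word of mouth and, in the age-matched cohort, may be up to 90 years old. OA patients come mainly from the hand clinics, where a clinical team member identifies them and may know their medicines. At stake is the safety of subjects in a study that, by section 8, offers them no direct benefit.

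**Working it through.** There is no figure in the plan to reproduce. The check is to follow one hypothetical subject through the stated steps: a woman aged 40 to 90 without hand pain who takes blood-thinning medicine and contacts the team after seeing the flyer.

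1. **Exclusion bullets (3).** They cover pregnancy, minority, mental disability and custodial status; other hand or wrist pathology; and uncontrolled diabetes, rheumatoid arthritis, muscular dysfunction or neurological disease. None mentions medicines or bleeding. She is not excluded.
2. **Phone questions (6).** They cover sex and age, arthritis, current pain, recent treated pain, vulnerable status, and systemic disease. Question (f) may catch some users of such medicine by chance, because it names stroke and diabetes, but it does not ask about medicine. If she has none of these conditions, she passes.
3. **Scheduling rule.** It depends on the answers to (a) to (f). No physician review is stated between the call and the visit.
4. **Consent.** Section 6 says of the in-person talk: "This discussion will include information on study purpose and procedures, benefits and risks". This describes giving information. It does not describe taking a medication history, though a subject may volunteer one.
5. **Session I arrival.** The data collected are age, sex, height, weight and limb length. These are descriptive data, not a screening step, and none of them concerns bleeding.
6. **Health-history form.** It is listed among the Session II questionnaires and described as a pain history. Its items are not shown. Questionnaires may be completed in either session and sessions may run in any order, so it need not come before the needle.
7. **Fine-wire placement.** A trained researcher places the electrodes in the biomechanics laboratory. The ceiling is 9 muscles × 3 attempts = 27 attempts per subject. Fewer will occur when placement succeeds early, a muscle is skipped or the subject stops.

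She therefore reaches step 7 without any stated step having asked the question or informed the physician. By contrast, for the anxiety and depression forms section 7 does write out such a route: they are scored before the session ends, and an elevated score leads to contact with a clinical co-investigator.

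**The case against.** The strongest reply is that this is an unwritten detail and not an error. The exclusion list is called a summary. Electrodes are placed under standard practice guidelines and best practices, and risks are discussed in person before any data collection. Any of these, or the health-history form, may already prompt the question, and the guidelines, consent text and form items are not available for review. All of that stands, and it is why the point is limited to what the protocol states.

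It is also true that the stated safeguards bear on the named risk: trained staff, sterile technique, ultrasound guidance, the attempt cap and the right to stop with full compensation. The sentence on the physician's discretion closes the paragraph on pain testing, so its reach to EMG is a matter of reading, although it speaks of participation in general. Finally, the protocol does not itself say that blood-thinning medicine raises the risk of fine-wire placement.

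What survives is narrower. The phone questions and the scheduling rule are set out explicitly, and following them as written books such a subject without the question being asked.

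A reader might infer that at-risk subjects will receive needles unchecked. The documents do not support this, because an unseen guideline or form may supply the check. A reader might also take the attempt ceiling, multiplied over a cohort, as the size of the hazard. It is not: it says nothing about how many women have a bleeding tendency.

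**Conclusion.** The point holds as a low-severity gap in subject safety. None of the 3 listed exclusion bullets and none of the 6 phone questions covers blood-thinning medicine or a bleeding disorder, and the physician's discretion has no stated route by which that information arrives before the needle.

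The conclusion rests on one assumption: that such medicine or such a disorder raises the risk of bleeding from needle insertion. This is ordinary medical knowledge, but the protocol does not state it or say by how much. The protocol calls these risks rare and gives no prevalence of use, so no count of affected women can be offered. It would go too far to conclude that the study's results are compromised: no estimate, comparison or sample-size figure depends on this.

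**What to change.** On both recruitment routes, at phone screening or at the latest before the first needle in Session I, ask: Do you take blood-thinning medicine or have a bleeding disorder? Refer any yes to the study physician, who decides whether to omit fine-wire placement for that subject. Keep surface EMG and all other tests.

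If a guideline, consent text or form already contains this check, it is enough to name it in section 6 and require it before placement.

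The cost is a brief amendment and one question per subject. The downside is a few lost intramuscular recordings, probably mostly in older subjects. The protocol already accepts that a muscle may go unrecorded after three failed attempts, and no subject is lost from the other measures.
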